6.5 Safety Assessments

6.5.1 Weight and Height

Height will be measured, and BMI will be calculated at Screening only with the subject wearing no shoes. Weight will be measured at all visits in fasting conditions when possible (on visits when subject is required to fast). Height will be measured at Screening only with the subject wearing no shoes, coats, jewelry and other accessories.

6.5.2 Vital Signs

Vital signs, including seated systolic/diastolic blood pressure (SBP/DBP), heart rate and oral temperature, will be recorded where indicated in Table 1. Vital signs will be measured after the subject has been sitting for at least 5 minutes in a quiet environment and prior to any blood draw

that occurs at the same time point. The recorded seated SBP/DBP value will be the mean of two measurements taken 2 minutes apart and always using the non-dominant arm.

6.5.3 Physical Examination

A complete physical examination will be performed at Screening and Visits 3 and 8. At the Investigator's discretion, an additional physical exam may be performed during the end of the study/early termination (Visit 9). The physical examination will include the following organ or body system assessments: skin; head, eyes, ears, nose, and throat; thyroid; lungs; cardiovascular; abdomen (liver, spleen); lymph nodes; and extremities, as well as an abbreviated neurological examination.

6.5.4 12-Lead ECG

A 12-lead ECG will be performed at Screening. At the Investigator's discretion, an additional ECG may be performed at the end of the study/early termination (Visit 9). The 12-lead ECG will be recorded after the subject has been resting at least 5 minutes in the supine position in a quiet environment. ECGs will be read for QT and QTc (Federicia's) intervals and clinically significant abnormalities.

6.5.5 Clinical Laboratory Tests

Blood for clinical safety laboratory assessments will be collected and processed using standard procedures at Screening and on Visits 3, 6, 7, 8 and 9 and on any unscheduled visit if the investigator deems it necessary. A local laboratory will perform all clinical laboratory tests. In the event of abnormal clinical laboratory values, the Investigator will make a judgment whether or not the abnormality is clinically significant.

6.5.5.1 Clinical Safety Laboratory Tests

The clinical safety laboratory tests will include the following hematology and serum chemistry tests:

- Hematology
 - Complete blood count (CBC)
- Serum Chemistry
 - Electrolytes
 - BUN
 - INR
 - Creatinine
 - Glucose level
 - Liver function tests (LFT) including transaminases (ALT, AST), albumin, and alkaline phosphatases, creatine phosphokinase (CPK), Bilirubin
 - Urine/serum pregnancy tests
 - TSH
 - FSH test if necessary

6.5.5.2 Additional Bloodwork

In addition to the blood tests listed above, viral serology (HCV-Ab, HBsAg, HBcore-total, HBs Ab, anti-HIV Ab), HbA1C, adiponectin and TSH will be measured according to Table 1.

6.5.6 Fasting Blood Glucose and Insulin Monitoring

During the study, both fasting finger stick glucose and laboratory fasting plasma glucose will be obtained at time points stated in Table 1. Fasting blood insulin will be used to determine HOMA estimates.

6.5.7 Pregnancy Test

A urine pregnancy test will be performed for women in child bearing years at Screening (Visit 1), Visit 2, Visit 3 and at Visits 6, 7, 8 and 9. A serum pregnancy test will be performed at Visit 3.

FSH testing to confirm menopause will be performed at Screening for women who have had more than 24 months since their last menstrual cycle, who are younger than 55 years old, and who are not surgically menopausal.

6.6 Review and Documentation of Medications and Supplements

All medications or supplements subjects are taking or have taken within 30 days prior to Visit 1 through Visit 9 will be recorded in the subject's medical record and the CRF.

All medications and supplements (other than IMP) taken by the subject after Visit 2 through Visit 8 assessments will be considered "concomitant" medications and supplements.

Medications and supplements taken prior to Visit 1 that are no longer being taken at Visit 1 will be considered "prior" medications and supplements.

Medications and supplements should be recorded according to the generic name when possible. The use of concomitant medications and supplements should be limited to those that are medically necessary. Any medication or supplement used should have an indication recorded, and for concomitant medications and supplements, this indication must be represented as either for the treatment of an AE, for the management of a pre-existing condition, or for prophylaxis.

Dosage increases for any concomitant medication or supplement should be noted and the reason for the dosage increase recorded as an AE (assumes worsening condition). The side effects of concomitant medications will be recorded as AEs.

Any subject whose condition becomes disqualifying during the course of the study may be treated for that condition. If the condition is suspected during Screening, the subject should not be enrolled. Treatment of the condition should be instituted according to the Investigator's/attending physician's judgment.

Medications that have no treatment intent but rather are part of supportive routine care such as local anesthetics, intravenous solutions to maintain fluid balance and keep access open, medications used for prophylaxis, and narcotics for postsurgical pain must also be recorded in the subject's medical record and CRF.

7 ADVERSE EVENTS AND SAFETY REPORTING

Information about all adverse events, whether volunteered by the patient, recorded in the patient's diary, discovered by Investigator questioning, or detected through physical examination, laboratory test or other means, will be collected and recorded on the Adverse Event Case Report Form and followed-up as appropriate.

Medical conditions present at study entry are considered pre-existing conditions and will be documented as medical history in the study source and CRF documents. All adverse events, including worsening of pre-existing conditions, must be reported and documented as described below.

7.1 Safety and Tolerability Assessments

Volunteered, observed, and elicited reports of adverse events must be recorded. This includes adverse events the patient reports spontaneously, those the Investigator observes, and those the study staff elicits in response to open-ended questions during study visits.

Each adverse event will be assessed by the Investigator with regard to seriousness, severity, and relatedness to the study treatment for recording in the CRF.

7.2 Definition of Adverse Event

An adverse event is any untoward medical event that occurs in a patient or patient administered a pharmaceutical product and that does not necessarily have a causal relationship with this treatment. An adverse event can therefore be any unfavorable and unintended sign (including abnormal laboratory findings), symptom, or disease temporally associated with the use of a medicinal (investigational) product, whether or not related to the medicinal (investigational) product.

7.3 Adverse Events of Special Interest

7.3.1 Adverse Events of Hypoglycemia

The CTCAE (version 5.0) criteria for mild, moderate, and severe hypoglycemia based on blood glucose will be used, as shown below:

Mild: < 70 – 55 mg/dL (< 3.8 - 3.0 mmol/L)

Moderate: < 55 – 40 mg/dL (< 3.0 - 2.2 mmol/L)

Severe: < 40 – 30 mg/dL (< 2.2 - 1.7 mmol/L)

Life Threatening: < 30 mg/dL (< 1.7 mmol/L)

7.4 Definition of Serious Adverse Event

International Conference on Harmonization (ICH) Guidelines define a serious adverse event (SAE) as any untoward medical occurrence that:

- Results in death.
- Is life-threatening.

- Requires or prolongs existing hospitalization.
- Results in persistent or significant disability or incapacity.
- Is a congenital anomaly or birth defect.
- Important medical events that may not result in death, be life-threatening or require hospitalization, but that may jeopardize the patient or require medical intervention to prevent one of the above outcomes, should also be considered serious when based upon the Investigator's medical judgment.

Events not to be reported as SAEs are the following:

- Routine treatment or monitoring of the studied indication, not associated with any deterioration in condition.
- Treatment, including hospitalization, which was elective or pre-planned for a pre-existing condition that is unrelated to the indication under study and did not worsen.
- Treatment on an emergency, outpatient basis for an event not fulfilling any of the aforementioned definitions of "serious" and not resulting in hospital admission.

7.5 Recording Adverse Events

All adverse events experienced during the trial, regardless of relationship to study medication, must be recorded on the Adverse Event CRF from the time of patient consent until completion of patients End of Study visit (Visit 9). All serious adverse events will be collected through Visit 9. The Investigator must continue to follow all non-serious events possibly related to the study medication and all serious adverse events until they resolve or until the Investigator assesses them in writing as chronic or stable.

Regardless of relationship to study medication, the event must be recorded on the Adverse Event CRF. Adverse event documentation should include the following information:

- Standard medical terminology for the AE
- Description of adverse event
- Date and time of onset
- Date and time of resolution of the adverse event
- Whether or not the event is ongoing
- Severity of the event
- Relationship between the adverse event and the investigational product
- Description of any actions taken (e.g., medications, treatments)
- Outcome of the AE
- Whether or not the effect was serious and/or unanticipated

Whenever possible, a diagnosis should be given when signs and symptoms are due to common etiology (e.g., cough, runny nose, sneezing, sore throat, and head congestion should be reported as "upper respiratory infection"). For the purposes of this study, hypoglycemic events will be considered adverse events and should be recorded in source and CRF records.

When a diagnosis is not available, each adverse event should be reported separately. For example, "nausea and vomiting" should be split into two separate events.

7.5.1 Routine Reporting of Adverse Events

All AEs, whether or not associated with the IMP that are observed by the Investigator, other Investigational Site personnel, or those reported by the subject will be recorded in the subject's source documentation and on the AE page of the CRF. Copies of the SAE CRF pages or an SAE listing generated based on the CRF pages will be submitted to the Sponsor at regularly scheduled intervals to allow the Sponsor to meet expedited regulatory reporting requirements under 21 CFR 312.32 and regular regulatory reporting requirements under 21 CFR 312.33.

For each AE, the following information will be entered in the CRF:

- Medical diagnosis of the event in standard medical terminology (if a medical diagnosis cannot be determined, a description of each sign or symptom characterizing the event);
- Date of onset of any new AE or worsening of a previously observed AE. For the days when the subject is in the clinic (Visit 2 to Visit 9), the time (based on a 24-hour clock) of onset should be recorded if available;
- Date of resolution of the event (or confirmation ongoing). For the days when the subject is in the clinic (Visit 2 to Visit 9), the time (based on a 24-hour clock) of resolution should be recorded if available;
- Whether the event is serious (per definition in Section 7.4), and if so, the reason it is considered serious;
- Severity of AE (per definition in Section 7.7);
- Assessment of the attributability of the AE to the IMP [per definition in Section 7.5];
- Whether the event is expected (per definition in Section 7.8);
- Action taken in treating the AE (including concomitant medications or therapies administered) and/or change in the IMP administration or dose (including whether the IMP was temporarily interrupted or discontinued);
- Outcome of AE (per definition in Section 7.9).

7.5.2 Reporting of Serious Adverse Events

In accordance with Federal regulations, Investigators will be notified of the occurrence of serious, unexpected and related adverse events.

The Investigator must report all serious adverse events to Sponsor or delegate within 24 hours of the site being notified of the event. Investigators must also report these events to the Institutional Review Board (IRB) in accordance with the IRB's reporting guidelines, within the IRB specified timeframe, or no later than 48 hours after knowledge of the event.

For submission of these events to the Israeli Regulatory Agency- the Sponsor will follow FDA regulations 21 CFR 312.32. If the event is determined to meet the requirements of IND Safety Reporting, then expedited reporting requirements to the FDA will be followed. The Sponsor may need to issue an Investigator notification, to inform all Investigators involved in any study with

the same drug (or therapy) that this serious unexpected suspected adverse reaction (SUSAR) has occurred.

Investigator Reporting Procedures

The PI or other study personnel must immediately (within 24 hours) inform Sponsor or delegate of any AE considered serious (as defined above) or otherwise medically significant. Notification should be via email or facsimile transmission of a written report signed by the PI. Notification must include the PI's assessment as to whether the event was or was not related to the use of the study medication. The Sponsor contact information is as follows:

Oramed Ltd.

[name]

Contact person at Oramed:

[name]

Email: [contact]

[contact]

The Principal Investigator must also promptly inform the governing IRB of the serious adverse event per the governing IRB's requirements.

The CRO will notify Oramed within 24 hours of receipt. Any SAE that occurred within 30 days after last dose will be followed and reported as above.

Pregnancy Reporting

If the subject or partner of a subject participating in the study becomes pregnant during the study or within 30 days of discontinuing study medication, the Investigator should report the pregnancy to Oramed within 24 hours of being notified. The Exposure In Utero form to the Investigator for completion.

The subject or partner should be followed by the Investigator until completion of the pregnancy. If the pregnancy ends for any reason before the anticipated date, the Investigator should notify the Sponsor. At the completion of the pregnancy, the investigator will document the outcome of the pregnancy. If the outcome of the pregnancy meets the criteria for immediate classification as an SAE (i.e., postpartum complication, spontaneous abortion, stillbirth, neonatal death, or congenital anomaly), the Investigator should follow the procedures for reporting an SAE.

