If either of the criteria listed below is met, enrollment of new subjects and dosing of ongoing subjects will be temporarily stopped. The Investigator, Sponsor, and the Medical Monitor will discuss whether a lower dose or any additional treatment guidelines should be implemented, or if the trial should be permanently stopped. Any proposed changes to the protocol to address such findings will be submitted for review and approval by the IEC/IRB and the Competent Authority prior to re-starting the trial.

1. A death within 30 days after IMP administration where there is a reasonable possibility that the drug caused the event;
2. Two Grade 4 AEs where there is a reasonable possibility that the IMP caused the events.

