7.6 Causality Assessment of Adverse Events

For all AEs, the Principal Investigator will provide an assessment of causal relationship to the study medication. The causality assessment must be recorded in the subject's source documents and on the AE CRF. Causal relationship will be classified according to the following criteria:

1. *Unrelated*: The event is clearly due to causes other than the active study drug.

2. *Unlikely*: The event is doubtfully related to active study drug. The event was most likely related to other factors such as the patient's clinical state, concomitant drugs or other therapeutic interventions.
3. *Possible*: The event follows a reasonable temporal sequence from the time of active study drug administration but could have been produced by other factors such as the patient's clinical state, therapeutic interventions or concomitant drugs.
4. *Probable*: The event follows a reasonable temporal sequence from the time of active study drug administration and follows a known response pattern to the drug. The toxicity cannot be reasonably explained by other factors such as the patient's clinical state, therapeutic interventions or concomitant drugs.
5. *Definite*: The event follows a reasonable temporal sequence from the time of active study drug administration, follows a known response pattern to the drug, cannot be reasonably explained by other factors such as the patient's condition, concomitant drugs or therapeutic interventions, AND either occurs immediately following active study drug administration, improves on stopping the study drug, or reappears on re-exposure.

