8.1 Sample Size

Up to 40 patients with NASH and Type 2 DM will be enrolled in this multi-center exploratory study. Approximately 20 patients will be enrolled at 2 sites in Israel, approximately 10 subjects will be enrolled at 3 or 4 sites in Belgium and 10 patients at 2 sites in the USA.

The treatment regimen will consist of a soft gelatin capsule containing 8 mg insulin, and 75 mg SBTI. Patients will take 2 capsules daily in the morning 30 to 45 minutes prior to breakfast.

The size of the study population was determined by reviewing the literature for pilot studies and was found to be sufficient to show trends of reducing liver fat content by MRI PDFF (MRI-Proton Density Fat Fraction) images and Fibroscan including CAP. This study is not powered for statistical significance.

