9.2 Case Report Forms

CRF's are provided for each patient. The site will be trained in the use and completion of the CRFs. All forms must be filled out as instructed by appropriate personnel who have undergone CRF training. Data will be entered into the CRF as information becomes available on a visit-by-visit basis. All data recorded on the CRF's should be supported by source documentation including completed patient diaries which will act as the source for this study. Only incidences where the data is only recorded once in the CRF will the CRF act as source and additional supporting source documentation is not warranted. The study completion information page of the CRF must be signed and dated by the Principal Investigator.

All CRF corrections are to be made by an Investigator or other study site personnel. The Principal Investigator or Sub-Investigator must authorize changes to the recorded safety and efficacy data, and this authorization must be documented in the source documents.

The Investigator or Sub-Investigator will sign and date the indicated places of the CRF. This signature will indicate that thorough inspection of the data therein has been made and will thereby certify the contents of the form. Documentation of procedures and visits will also be maintained in source documents and signed by the Investigator or Sub-Investigator.

CRFs will be scanned and later mailed to the sponsor in Israel.

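### Halting criterion 2 counts related Grade 4 events across 7 or 8 sites, but a Grade 4 event judged neither serious nor medically significant has no timed route to the sponsor, and no role keeps the count

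*Combined protocol and SAP*

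**What the plan says.** Section 4.3 lists two criteria, either of which means that "enrollment of new subjects and dosing of ongoing subjects will be temporarily stopped". The first is a death. The second is "Two Grade 4 AEs where there is a reasonable possibility that the IMP caused the events". Once a criterion is met, "The Investigator, Sponsor, and the Medical Monitor will discuss whether a lower dose or any additional treatment guidelines should be implemented", or whether to stop the trial for good. The section does not say who establishes that a criterion has been met.

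Section 7.5.2 sets the fast route. The investigator or other study personnel "must immediately (within 24 hours) inform Sponsor or delegate of any AE considered serious (as defined above) or otherwise medically significant". The recipient is the sponsor or its delegate; the Medical Monitor is not named there.

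For other adverse events, Section 7.5.1 has everything recorded on the CRF but sends only SAE pages or an SAE listing to the sponsor at regular intervals, whose length is not given. Section 9.2 adds that "CRFs will be scanned and later mailed to the sponsor in Israel", with no time limit.

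On causality, Section 7.6 states: "Causal relationship will be classified according to the following criteria", and then gives five categories from unrelated to definite.

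On sites, Section 8.1 plans: "Approximately 20 patients will be enrolled at 2 sites in Israel, approximately 10 subjects will be enrolled at 3 or 4 sites in Belgium". Two US sites are to supply the last 10.

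**The concern.** A stopping rule works only if the facts it needs reach someone who can apply it. This one needs two facts about each event, its grade and its relation to the drug, and a total across all sites. The fast reporting duty is keyed to a third attribute, seriousness, with an undefined extension for medical significance. Section 7.5.1 itself has the site record seriousness and severity as separate items, so the protocol does not treat one as implying the other.

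This is one of only two rules in Section 4.3 that pause treatment for every patient, in a trial whose primary objective is safety. If a qualifying event arrives late, patients at other sites go on being dosed, and new ones enrolled, after the protocol's own condition for a pause has been met. No site need have broken any reporting instruction for this to happen.

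**Working it through.** The plan states no operating characteristic for the halting rule, so there is no figure to reproduce. The check traces one event through the text; a short calculation then gives context.

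**1. The attributes compared**
- Halting criterion 2 (4.3): Grade 4, with a reasonable possibility of drug causation, counted over the trial.
- Fast route (7.5.2): serious, or medically significant.
- Seriousness (7.4): includes life-threatening events and, at the investigator's judgement, other important medical events. Grade is not among the criteria.

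The sets overlap heavily but are not the same, and no section says that Grade 4 implies serious or medically significant.

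**2. Routes open to a related Grade 4 event judged neither serious nor medically significant**
- 7.5.2: not triggered.
- 7.5.1 periodic submission: SAE pages or listings only.
- 9.2: CRFs scanned and mailed later, no limit.
- 9.5: telephone contact and on-site CRF review by the study monitor; described as frequent, but no interval is set.
- 4.3: consultation with the sponsor and Medical Monitor before a subject is removed (emergencies excepted), and their approval before drug interrupted for an adverse event is restarted. Applies only if the event leads to one of these.
- 5.6: contact with both if the subject needs medication. Applies only in that case.

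An abnormal laboratory value that leads to no medication, interruption or removal triggers none of the last two. Every route that remains is without a deadline.

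**3. Who counts**
Section 4.3 names those who confer after a criterion is met. Neither it nor Section 7 gives anyone the task of keeping the total.

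**4. Can the count be made from what sites record?**
- Severity: 7.5.1 sends the site to the 7.7 scale, which has three levels and ends at severe. Section 8.2.1 grades by CTCAE version 4.03. Section 7.3.1 uses version 5.0 for hypoglycaemia, with four bands. For a general adverse event the site's scale has no Grade 4.
- Causality: the rule uses a reasonable-possibility test, 7.6 uses five categories, and the 7.5.2 notice asks for a yes-or-no statement of relatedness. No section maps one to another, and 7.5.1 points to Section 7.5 for attribution although the categories are in 7.6.

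**5. Context: would one site see both events?**
Inputs from 8.1: 20 patients at 2 Israeli sites, 10 at 3 or 4 Belgian sites, 10 at 2 US sites. Sites: 2 + 3 + 2 = 7, or 2 + 4 + 2 = 8. Patients: 20 + 10 + 10 = 40. Assumptions: full enrolment, an even split within country, equal risk per patient, and the two events in different patients.

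P(different sites) = 1 − (same-site pairs) / C(40,2), with C(40,2) = 780.
- Israel: 2 × C(10,2) = 90. USA: 2 × C(5,2) = 20.
- Belgium, 3 sites (4, 3, 3): 6 + 3 + 3 = 12. Belgium, 4 sites (3, 3, 2, 2): 3 + 3 + 1 + 1 = 8.
- 7 sites: 1 − 122/780 = 0.844. 8 sites: 1 − 118/780 = 0.849.

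So two affected patients would usually be at different sites, and the total has to be kept centrally.

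**The case against.** The strongest reply is that the existing text already catches most such events. Life-threatening events are serious under 7.4, and the extension to medically significant events carries the 24-hour duty beyond SAEs. Several untimed contacts also exist under 4.3, 5.6 and 9.5. All of that stands, and it makes the gap narrow. It does not close it: medical significance is left to each site, and the other contacts have no deadline.

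Three stronger readings are tempting, and the documents do not support them.
- A reader might infer that the criterion could be met with nobody aware of any of it. Each site knows its own events; what can be late is recognition of the total. Nor is the mailed CRF the only other route, as the contacts listed above show.
- A reader might take a home glucose reading below 30 mg/dL as the typical missed event. Section 7.3.1 labels that band life-threatening, and a site reading it with 7.4 would plausibly report it as serious. A severity label is not strictly the seriousness criterion, but a laboratory-defined event is the better example.
- A reader might take 84–85% as the chance that the rule fails. It is not. It applies equally to serious events, which are reported promptly; it leaves out two events in one patient, which the criterion does not exclude; and it says nothing about how often a Grade 4 event would be judged neither serious nor medically significant.

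It can also be said that the lack of a causality mapping is a drafting matter separate from timing. That is fair. It belongs here only because whoever keeps the count needs one definition.

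**Conclusion.** The point holds in a limited form. The text allows a related Grade 4 event to go without timed notice to the sponsor, and it gives no one the cross-site count, so a trial-wide pause can be recognised late with every site in compliance. The death criterion is unaffected, because death is serious by definition. No sample size or error rate changes.

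The frequency of the problem cannot be estimated: the documents give no rate for related Grade 4 events, nor the share that would be judged neither serious nor medically significant. The 84–85% figure rests on the assumptions stated with it and supports only the need for a central count. The change is worth making because it is cheap and makes an existing safety rule workable.

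**What to change.** - **Section 7.5.2:** add that any adverse event at the severity level used in halting criterion 2 that may be related to the study drug is notified to the sponsor and the Medical Monitor within 24 hours, whether or not it is serious.
- **Section 4.3:** name the role that keeps the running count across sites.
- **Reconcile the severity scales** in 7.3.1, 7.5.1, 7.7 and 8.2.1 with criterion 2, so that sites record the level it counts. The first change depends on this.
- **Reconcile the causality terms** in 4.3, 7.5.2 and 7.6, and correct the cross-reference in 7.5.1.

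Which scale applies, and which causality categories satisfy the criterion, is for the sponsor to state; nothing here proposes a different halting rule. The cost is two added sentences, the reconciling edits, and a few extra 24-hour notices, which could use the existing SAE notification procedure.
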